3.2.1.2. Radiological Response

Radiological Response based on DRC Assessment at EOST will be categorized as follows:

- Complete response: Resolution (normalization of X-ray, CT scan, etc.) of all radiological abnormalities attributed to aspergillosis compared to Baseline.
- Partial response: Major improvement of radiological abnormalities attributed to aspergillosis compared to Baseline.
- Stable disease: Minor or no improvement of radiological abnormalities attributed to aspergillosis compared to Baseline.

• Failure: Worsening of radiological abnormalities attributed to aspergillosis compared to Baseline.

3.2.1.3. Mycological Response

Mycological Response based on DRC Assessment at EOST will be categorized as follows:

- Eradication: Absence of Aspergillus (or other mold) in a relevant clinical specimen (culture negative and absence of fungal elements by microscopy or histopathology, as appropriate).
- Presumed eradication: Inferred in patients with complete clinical and imaging response for whom an invasive procedure for obtaining the relevant clinical specimen is not performed.
- Persistence: Any evidence based on culture, microscopy, or histopathology for the presence of *Aspergillus* (or other mold).
- Indeterminate: Inadequate data available for categorization as eradication, presumed eradication, or persistence.

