#### Aspergillosis only

Cl antigen

Antigen detected in plasma, serum, BAL, or CSF

- Any 1 of the following:
  - Single serum or plasma:  $\geq 1.0$
  - BAL fluid:  $\geq 1.0$
  - Single serum or plasma:  $\geq 0.7$  and BAL fluid  $\geq 0.8^*$
  - CSF: ≥1.0

Aspergillus PCR\*

Any 1 of the following:

- Plasma, serum, or whole blood: 2 or more consecutive PCR tests positive
- BAL fluid: 2 or more duplicate PCR tests positive
- At least 1 PCR test positive in plasma, serum, or whole blood and 1 PCR test positive in BAL fluid

Aspergillus species recovered by culture from sputum, BAL, bronchial brush, or aspirate

\*Patients with the following preliminary mycological evidence may be entered into the study:

- 1. A single serum or plasma CCl ≥0.7 or CCl in BAL fluid ≥0.8 pending the results of a second CCl test collected prior to dosing.
- 2. A single positive PCR for *Aspergillus* from plasma, serum, whole blood, or BAL pending the results of a second PCR test collected prior to dosing.
- 3. A positive result from the Karius test which indicates the presence of cell-free DNA for *Aspergillus* or other rare molds.
- 4. A positive result from IMMY's sona *Aspergillus* Lateral Flow Device pending the results of a CCI or PCR test for *Aspergillus*.

After inclusion into the study, every effort should be made to upgrade the certainty of diagnosis of IFD. BAL = bronchoalveolar lavage; CSF = cerebrospinal fluid; CT = computed tomography; GVHD = graft versus host disease; IFD = invasive fungal disease; PCR = polymerase chain reaction; spp. = species; STAT 3 = signal transducer and activator of transcription 3; TNF = tumor necrosis factor. (Donnelly et al.,2019)

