# APPENDIX G: RESPONSE CRITERIA

Outcome, Response	Criteria
Success	
Complete response	Survival within the prespecified period of observation, resolution of all attributable symptoms and signs of disease and radiological abnormalities, and mycological evidence of eradication of disease
Partial response	Survival within the prespecified period of observation, improvement in attributable symptoms and signs of disease and radiological abnormalities, and evidence of clearance of cultures or reduction of fungal burden, as assessed by a quantitative and validated laboratory marker
Failure	
Stable response[1]	Survival within the prespecified period of observation and minor or no improvement in fungal disease, but no evidence of progression, as determined on the basis of a composite of clinical, radiological, and mycological criteria
Progression of fungal disease	Evidence of progressive fungal disease based on a composite of clinical, radiological, and mycological criteria
Death	Death during the prespecified period of evaluation, regardless of attribution

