## **Mycological Response**

Mycological Response to Treatment will be Categorized as One of the Following 4 Possible Outcomes:	
Eradication	Absence of Aspergillus in a relevant clinical specimen (culture
	negative and absence of fungal elements by microscopy or
	histopathology, as appropriate)
Presumed eradication	Inferred in patients with complete clinical and imaging response for
	whom an invasive procedure for obtaining the relevant clinical
	specimen is not performed
Persistence	Any evidence based on culture, microscopy, or histopathology for
	the presence of Aspergillus
Indeterminate	Inadequate data available for categorization as eradication, presumed
	eradication, or persistence

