6.4.3. Mycological Response

Mycological responses will be assessed by DRC and by investigator and will be classified as eradication, presumed eradication, persistence, or indeterminate.

Number and percentage of patients in the mITT Populations with mycological responses at EOST as determined by the DRC will be tabulated for Cohort A. Two-sided 80% exact binomial CIs of the treatment success (eradication and presumed eradication) rate will be presented for Cohort A.

Mycological responses at EOST as determined by the Investigator will be tabulated in the same manner.

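### Mycological Eradication does not require a positive baseline specimen, so the whole-mITT success rate mixes observed clearance with specimens that were never positive, and the direction of the distortion is not fixed

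*SAP*

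**What the plan says.** **Outcome scale.** SAP 3.2.1.3 (DRC assessment at EOST) defines Eradication as "Absence of Aspergillus (or other mold) in a relevant clinical specimen", established by "culture negative and absence of fungal elements by microscopy or histopathology, as appropriate". Protocol Appendix G has the same construction ("Absence of Aspergillus in a relevant clinical specimen (culture"), and so does the Investigator version in SAP 3.2.1.7. Persistence is "Any evidence based on culture, microscopy, or histopathology for the presence of" the mold. Indeterminate is "Inadequate data available for categorization as eradication, presumed eradication, or persistence". Presumed eradication covers patients with complete clinical and imaging response in whom no invasive sampling was done.

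**Entry.** For probable aspergillosis, the Aspergillosis-only part of Protocol Appendix E accepts as mycological evidence "Antigen detected in plasma, serum, BAL, or CSF" above stated thresholds. It also accepts defined PCR results. Neither route needs a positive culture or microscopy. SAP section 4 admits DRC-confirmed proven or probable cases to the Cohort A mITT.

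**Analysis.** SAP 6.4.3 tabulates mycological response in the mITT and gives a two-sided 80% exact interval for the "treatment success (eradication and presumed eradication) rate", by DRC and again by Investigator. SAP 5.4 keeps patients with missing outcomes in the efficacy denominators.

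**Sampling.** After Screening, fungal cultures (Protocol 7.5.5) and BAL (7.5.4) are taken only when clinically indicated. Pathogen PCR is scheduled at Screening only (7.5.1 and Appendix A).

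**The concern.** Entry and outcome rest on different evidence. A patient can be diagnosed on serum antigen with a BAL that is already negative by culture and microscopy. Another negative specimen at EOST then fits Eradication, although nothing has changed by the measure being scored. Persistence cannot be assigned on antigen or PCR, so a marker that stays positive does not alter the category. No rule sends this patient to Indeterminate, which is reserved for inadequate data.

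The mycological scale is the odd one out here. The clinical and radiological scales (SAP 3.2.1.1 and 3.2.1.2) both measure change against Baseline. The SAP also defines a culture-based baseline pathogen (3.5 and 5.3.3), but 6.4.3 does not use it to restrict this endpoint.

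At stake is what the mycological success rate means. As defined, it cannot be read as the share of patients whose infection was cleared. Mycology also contributes to the secondary endpoint, because a global complete response calls for "mycological evidence of eradication of disease".

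**Working it through.** **The plan's own figure.** SAP 2.4 gives 60% of about 40 dosed patients: 0.60 × 40 = 24 in the mITT. Its power statement reproduces. Rejecting at 7 or fewer deaths of 24 has exact one-sided alpha P(X ≤ 7 | 24, 0.45) = 0.086 and power P(X ≤ 7 | 24, 0.20) = 0.911. Eight deaths would give alpha 0.173. I use only the denominator of 24 from here on.

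**How an antigen/PCR-only patient is classified at EOST under the text**

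| Situation at EOST | Category | Effect on the SAP 6.4.3 rate |
|---|---|---|
| Specimen taken, negative | Eradication | success |
| No invasive specimen, complete clinical and imaging response | Presumed eradication | success |
| No specimen, response not complete | Indeterminate | in denominator, not success |
| Culture, microscopy or histopathology positive | Persistence | in denominator, not success |

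**Formula.** Let b be the number of baseline-positive patients, x of whom clear. Let m be the number of antigen/PCR-only patients, k of whom are scored as successes.

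- Reported rate = (x + k)/(b + m).
- Rate where clearance can be observed = x/b.
- The two are equal when k = m·x/b. A larger k inflates the reported rate and a smaller k deflates it.

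**Illustration (assumed: b = 16, x = 6, m = 8).** Intervals are Clopper-Pearson, two-sided 80%.

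- k = 0: 6/24 = 25% (14–40%).
- k = 3, the break-even (8 × 6/16 = 3): 9/24 = 37.5% (24–53%).
- k = 8: 14/24 = 58% (43–72%).
- Observable clearance: 6/16 = 37.5% (21–57%).

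Each antigen/PCR-only patient scored as a success adds 1/24, about 4 percentage points.

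**Other case mixes (assumed: 24 patients, half of the baseline-positive patients clear)**

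| Antigen/PCR-only | Observable rate (80% CI) | Reported, k = 0 | Reported, k = all |
|---|---|---|---|
| 6 | 9/18 = 50% (33–67%) | 9/24 = 37.5% | 15/24 = 62.5% |
| 12 | 6/12 = 50% (29–71%) | 6/24 = 25.0% | 18/24 = 75.0% |
| 18 | 3/6 = 50% (20–80%) | 3/24 = 12.5% | 21/24 = 87.5% |

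With true clearance held at 50%, the reported figure can run from 12.5% to 87.5%, driven only by case mix and by who is resampled.

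**The case against.** **The rate is not necessarily inflated.** A reader might infer that every antigen/PCR-only patient is counted as a success and that the rate is biased upward. The documents do not support this. A success needs either a negative specimen, when follow-up cultures are only clinically driven, or a complete clinical and imaging response. Otherwise the patient is Indeterminate and lowers the rate. This objection stands in full.

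**The criterion is stricter than one negative test.** Eradication asks for a negative culture and also no fungal elements by microscopy or histopathology, as appropriate. That is correct, but a patient negative on all of these before dosing still meets it afterwards.

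**The effect on global response is limited.** A reader might also infer that the secondary endpoint is seriously compromised. Complete response also needs resolution of attributable symptoms, signs and radiological abnormalities. A patient who achieves that without invasive sampling is already presumed eradicated. Partial response needs clinical and radiological improvement and, besides culture clearance, allows reduced fungal burden on a quantitative validated marker. This stands.

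**The DRC Charter may hold a baseline rule.** The Charter is not among the documents, and the notion of a relevant specimen leaves room for judgement. If such a rule exists, it belongs in the SAP. It would not obviously bind the Investigator assessment, which is tabulated in the same way. Some biomarker sections are also redacted, so a separate marker analysis may exist.

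**Listings identify culture-positive patients.** SAP 6.8.1 tabulates baseline pathogens and 6.4.7 lists cultures by subject. That helps a careful reader, but it does not give a rate with the right denominator.

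**Conclusion.** The definition has a real gap. As written, a patient who was never positive by culture, microscopy or histopathology can be scored as eradicated, and the whole-mITT rate in SAP 6.4.3 mixes such patients with observed clearances. The direction of the distortion depends on case mix and on clinically driven sampling. Under the main illustration, the reported rate lies between 25% and 58% against 38% where clearance can be observed.

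The mITT size of 24 is the plan's. The share of antigen/PCR-only patients and the clearance rate are my assumptions, since the documents give neither. The conclusion that the rate cannot be read as clearance needs only that some mITT patients lack a positive baseline specimen, which Appendix E permits.

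SAP Appendix 1 classes mycological response as Other, and it is reported descriptively. The primary mortality test is untouched and any effect on global response is bounded. A clarification should be made, but the trial's main conclusion does not depend on it.

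**What to change.** 1. In SAP 3.2.1.3, SAP 3.2.1.7 and Protocol Appendix G, assign Eradication only to patients with a baseline specimen positive by culture, microscopy or histopathology. Code a negative specimen in any other patient as Indeterminate (no positive baseline specimen).
2. In SAP 6.4.3, report the success rate and its 80% exact interval in the baseline-positive subset, with that denominator stated. Show antigen/PCR-only patients on a separate row, for both the DRC and the Investigator tables.
3. Give the DRC the same instruction, including where mycology feeds global response, and align it with the Charter.

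I would not make scoring on the baseline marker the general rule. Serial serum biomarkers are drawn through EOST (Protocol 7.5.3), but PCR is scheduled only at Screening and BAL only when clinically indicated. Patients diagnosed by PCR alone or by BAL antigen alone therefore have no scheduled follow-up of the marker that defined them.

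The cost is wording, one extra table row and one DRC instruction, with no new samples. The main row rests on fewer patients and is less precise. In the illustration, the 80% interval for 6/16 is about 36 points wide (21.0–56.5%), against about 29 points for 14/24 (43.3–72.3%).

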3.2.1.4. Investigator Assessment of Global Response

Global response based on investigator assessment at EOST are as follows:

- Complete Response: Survival within the prespecified period of observation, resolution of all attributable symptoms and signs of disease and radiological abnormalities, and mycological evidence of eradication of disease).
- Partial Response: Survival within the prespecified period of observation, improvement in attributable symptoms and signs of disease and radiological abnormalities, and evidence of clearance of cultures or reduction of fungal burden, as assessed by a quantitative and validated laboratory marker categorized as treatment success.
- Stable Response: Survival within the prespecified period of observation and minor or no improvement in fungal disease, but no evidence of progression, as determined based on a composite of clinical, radiological, and mycological criteria, progression of disease, or death (categorized as treatment failure).
- Progression of fungal disease: Evidence of progressive fungal disease based on a composite of clinical, radiological, and mycological criteria.
- Death: Death during the prespecified period of evaluation, regardless of attribution. If any patient has missing global response at EOST, it will be presented as 'Indeterminate' in the summary.

- Treatment Outcomes for Global Response based on Investigator Assessment at EOST:
 - Treatment success: Complete response or partial response.
 - Treatment failure: Stable response, progression of fungal disease and death.

3.2.1.5. Investigator Assessment of Clinical Response

Clinical response based on investigator assessment at EOST are as follows:

- Complete response: Resolution of all attributable symptoms, signs, and/or bronchoscopic abnormalities present at Baseline.
- Partial response: Major improvement (usually nearly complete) in attributable symptoms, signs, and/or bronchoscopic abnormalities present at Baseline.
- Stable response: Minor or no improvement in attributable symptoms, signs, and/or bronchoscopic abnormalities present at Baseline, but patient continued on therapy without deterioration.
- Failure: Deterioration in attributable symptoms, signs, and/or bronchoscopic abnormalities necessitating alternative antifungal therapy or resulting in death.

3.2.1.6. Investigator Assessment of Radiological

Radiological response based on investigator assessment are as follows:

- Complete response: Resolution (normalization of X-ray, CT scan, etc.) of all radiological abnormalities attributed to aspergillosis compared to Baseline.
- Partial response: Major improvement of radiological abnormalities attributed to aspergillosis compared to Baseline.
- Stable disease: Minor or no improvement of radiological abnormalities attributed to aspergillosis compared to Baseline.
- Failure: Worsening of radiological abnormalities attributed to aspergillosis compared to Baseline.

3.2.1.7. Investigator Assessment of Mycological Response

Mycological Response based on Investigator Assessment at EOST as Follows:

• Eradication: Absence of *Aspergillus* in a relevant clinical specimen (culture negative and absence of fungal elements by microscopy or histopathology, as appropriate).

- Presumed eradication: Inferred in patients with complete clinical and imaging response for whom an invasive procedure for obtaining the relevant clinical specimen is not performed.
- Persistence: Any evidence based on culture, microscopy, or histopathology for the presence of *Aspergillus*.
- Indeterminate: Inadequate data available for categorization as eradication, presumed eradication, or persistence.

3.2.1.8. Clinical Signs and Symptoms

Clinical signs and symptoms included Cough, Dyspnea, Pleuritic Chest Pain, Fever, Hemoptysis, Visual Disturbance, Skin Lesion, Headache, Sinus Pain, Joint Pain and/or swelling. Clinical signs and symptoms were assessed as absent, mild, moderate, severe or not done. ("Not done" is recorded at the symptoms level).

3.2.1.9. Next-generation Sequencing of Cell-free Pathogen DNA

DNA sequencing was performed by a reference genetic laboratory (Karius) to facilitate the identification of infecting pathogens; a subject level listing will be provided.

3.2.1.11. Fungal Culture

Fungal cultures were assessed at local clinical labs (investigator site). Isolated pathogens were sent to a central LAB (JMI Labs) for confirmatory identification and susceptibility testing. Subject level listing by subject by pathogen will be provided for local LAB and central LAB results.

3.2.1.12. Radiology Assessments

Radiology assessments were performed at screening, Day 14 and at EOST, and if clinically indicated on Days 7, 21, 28, 35, and 42; at the Follow-Up Visit; and at the E/T Visit (if applicable). Subject level listing of imaging will be provided.

3.4. Pharmacokinetic Assessments

Plasma samples for PK (fosmanogepix [prodrug] and manogepix [active moiety]) will be collected predose and 3 hours post start of infusion on Days 1 (Baseline), 2, 3, 7, and 14; predose on Days 28 and 42; and at any time in clinic at EOST, the Follow-Up Visit, and the E/T Visit (if applicable). Additionally, for patients who switch to PO dosing, samples should be collected predose and at 3 hours postdose on the initial day of PO dosing, Day 7, and Day 14 and at any time in clinic on Days 28 and 42, at EOST, at the Follow-Up Visit, and at the E/T Visit (if applicable). If the patient switches back to IV dosing, PK samples should be collected predose and at 3 hours post start of infusion on that day as well.

Optionally, if body fluids are sampled as part of routine patient management (eg, BAL, lumbar puncture, paracentesis, vitreal fluid collection, abscess drainage), within approximately 2 hours of blood sampling for PK, these samples may be stored for future analysis of fosmanogepix and manogepix levels.

3.5. Baseline Variables

Baseline data will be collected according to the schedule of procedures in the protocol.

For all efficacy and safety endpoints, baseline is defined as the last measurement or assessment prior to first dose of study drug.

For microbiological data, baseline pathogen(s) are *Aspergillus* spp. or rare molds (eg, *Scedosporium* spp., *Fusarium* spp., *Lomentospora* spp., and Mucorales fungi, etc.) isolated from the last positive fungal culture sample collected prior to the first dose of study drug.

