# APPENDIX D: REVISION AND UPDATE OF THE CONSENSUS DEFINITIONS OF PROVEN INVASIVE FUNGAL DISEASE FROM THE EORTC/MSGERC

Analysis and Specimen	Molds 
Microscopic analysis: sterile material	Histopathologic, cytopathologic, or direct microscopic examination  of a specimen obtained by needle aspiration or biopsy in which hyphae are seen accompanied by evidence of associated tissue damage
Culture	
Sterile material	Recovery of a hyaline or pigmented mold by culture of a specimen obtained by a sterile procedure from a normally sterile and clinically or radiologically abnormal site consistent with an infectious disease process, excluding bronchoalveolar lavage fluid, a paranasal or mastoid sinus cavity specimen, and urine
Blood	Blood culture that yields a mold  (eg, Fusarium species) in the context of a compatible infectious disease process
Serology	Not applicable
Tissue Nucleic Acid Diagnosis	Amplification of fungal DNA by PCR combined with DNA sequencing when molds are seen in formalin-fixed paraffin-embedded tissue

1. If culture is available, append the identification at the genus or species level from the culture results.

2. Tissue and cells submitted for histopathologic or cytopathologic studies should be stained using Grocott-Gomori methenamine silver stain or periodic acid Schiff stain to facilitate inspection of fungal structures. Whenever possible, wet mounts of specimens from foci related to invasive fungal disease should be stained with a fluorescent dye (eg, calcofluor or blankophor).

3. Recovery of *Aspergillus* species from blood cultures rarely indicates endovascular disease and almost always represents contamination.

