BAL = bronchoalveolar lavage; CSF = cerebrospinal fluid; CT = computed tomography; GVHD = graft versus host disease; IFD = invasive fungal disease; PCR = polymerase chain reaction; spp. = species; STAT 3 = signal transducer and activator of	
transcription 3; TNF = tumor necrosis factor.	

Mycological Evidence\*

- Any mold (*Aspergillus, Fusarium, Scedosporium* species., or Mucorales) recovered by culture from sputum, BAL, bronchial brush, or aspirate
- Microscopical detection of fungal elements in sputum, BAL, bronchial brush, or aspirate indicating a mold Tracheobronchitis
  - Aspergillus recovered by culture of BAL or bronchial brush
  - Microscopical detection of fungal elements in BAL or bronchial brush indicating a mold

Sino-nasal diseases

- Mold recovered by culture of sinus aspirate samples
- Microscopical detection of fungal elements in sinus aspirate samples indicating a mold

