6.7. Subset Analyses

The following sub-group analysis will be provided for primary and key secondary endpoint:

- Primary endpoint: Day 42 mortality by baseline pathogen.
- Secondary endpoint: global response at EOST by baseline pathogen.
- Primary endpoint: Day 42 mortality by limited treatment option criteria.
- Secondary endpoint: global response at EOST by limited treatment criteria.
- Primary endpoint: Day 42 mortality by participant who switch to 400 mg BID fosmanogepix dose vs. maintained with 800 mg of fosmanogepix dose QD.
- Secondary endpoint: global response at EOST by participant who switch to 400 mg BID fosmanogepix dose vs. maintained with 800 mg of fosmanogepix dose QD.

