6.8.1. Baseline Infection Characteristics

All baseline pathogens will be summarized with counts and percentages of patients in total for the mITT Populations.

Details of organism identification and antifungal susceptibility results including MICs of all antimicrobials tested will be listed by patient. Data from both local and central microbiological laboratories will be listed.

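### Taking baseline pathogen only from the last positive pre-dose culture lets a later airway isolate replace a sterile-site one in the by-pathogen summaries

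*SAP*

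**What the plan says.** SAP 3.5 (Baseline Variables) opens the microbiological rule with "For microbiological data, baseline pathogen(s) are" and then limits the organisms to those "isolated from the last positive fungal culture sample collected prior to the first dose of study drug". Section 5.3.3 repeats the rule. Neither section ranks specimen types, combines samples, sets a look-back window or refers to the DRC.

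The label is used in three places:
- SAP 6.7: "Primary endpoint: Day 42 mortality by baseline pathogen".
- SAP 6.7: "Secondary endpoint: global response at EOST by baseline pathogen".
- SAP 6.8.1: "All baseline pathogens will be summarized with counts and percentages of patients in total for the mITT Populations".

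The protocol treats culture sources differently. Appendix D gives proven status to "Recovery of a hyaline or pigmented mold by culture of a specimen obtained by a sterile procedure" from a normally sterile, abnormal site, "excluding bronchoalveolar lavage fluid, a paranasal or mastoid sinus cavity specimen, and urine". Appendix E accepts a mold "recovered by culture from sputum, BAL, bronchial brush, or aspirate" as mycological evidence for probable disease.

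**The concern.** Recency suits a vital sign or a laboratory value. It does not identify the organism causing an infection. A patient can enter the modified intent-to-treat (mITT) population as a proven case on a mold from sterile tissue and then be tabulated under a different mold from a sputum or lavage sample taken a day or two later. A mold that grew only in an earlier sample disappears from the label altogether.

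The rare-mold question makes this matter. Rare molds are in the study title and the primary objective, and Protocol 5.2 says that formal PK-PD work for them has not been done. The two by-pathogen lines in SAP 6.7 are the only planned efficacy summaries split by organism, and the rare-mold rows are likely to be small.

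**Working it through.** **1. Can a patient have several pre-dose cultures?** Yes.
- Protocol 6.2 collects fungal cultures at Screening (Day -5 to Day -1).
- Protocol 7.5.5 accepts standard-of-care cultures taken in the 120 hours before dosing.
- Protocol 6.3.1 adds Day 1 cultures when clinically indicated; those taken before the first infusion count as pre-dose.
- Appendix A, footnote f, allows a historical classification of proven or probable disease, so the diagnosing sample may come before the Screening sample.

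**2. What does the rule do in each case?**

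| Pre-dose cultures | Label under SAP 3.5 | Effect |
|---|---|---|
| Two molds in the last positive sample | Both | None lost |
| Tissue positive, later airway culture negative | Tissue mold | Correct |
| Airway mold first, different tissue mold later | Tissue mold | Sterile-site isolate kept, airway mold dropped |
| Tissue mold first, different airway mold later | Airway mold | Sterile-site isolate replaced |
| Two airway samples, different molds | Later mold only | Earlier mold dropped |
| Tissue mold first, later *Aspergillus* blood culture | *Aspergillus* | Replaced by a finding that Appendix D, note 3, regards as nearly always contamination |

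A replacement changes a table only if the two molds fall in different rows.

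**3. Does it touch the primary analysis?** The plan's figure is power above 90% with 24 mITT patients, 45% against 20% mortality, one-sided alpha 0.1, exact binomial (SAP 2.4 and 5.2). The cut-off is 7 deaths or fewer:
- size = P(X ≤ 7 | n = 24, p = 0.45) = 0.0863 (8 deaths would give 0.173);
- power = P(X ≤ 7 | n = 24, p = 0.20) = 0.9108.

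The stated power reproduces. The test counts deaths in all mITT patients whatever the organism, so the label cannot alter it.

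**4. How far can one relabelled patient move a subgroup?** Take a subgroup of k patients with d deaths and remove one patient.
- If that patient died: d/k − (d−1)/(k−1) = (k−d)/[k(k−1)], largest at d = 1, where it equals 1/k.
- If that patient survived: d/(k−1) − d/k = d/[k(k−1)], largest at d = k−1, where it equals 1/k.

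So 1/k is an upper bound. The same algebra applies to the response rate.

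**5. Illustration.** The documents give no pathogen mix. Assume 24 mITT patients with 5 deaths overall, and move one rare-mold patient to *Aspergillus*.

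| Assumed rare-mold subgroup | Before | Moved patient died | Moved patient survived |
|---|---|---|---|
| 2 deaths in 4 | 50.0% | 1/3 = 33.3% | 2/3 = 66.7% |
| 2 deaths in 6 | 33.3% | 1/5 = 20.0% | 2/5 = 40.0% |
| 3 deaths in 8 | 37.5% | 2/7 = 28.6% | 3/7 = 42.9% |

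In the middle row, *Aspergillus* mortality goes from 3/18 = 16.7% to 4/19 = 21.1% or 3/19 = 15.8%. Overall mortality stays at 5/24 = 20.8% throughout.

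**The case against.** The case against giving this much weight is substantial, and most of it limits the scope.

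- **Narrow trigger.** The patient needs at least two positive pre-dose cultures growing different molds, with one mold absent from the last positive sample. Pre-dose sampling is short, and nothing in the documents shows how often this happens. This stands.
- **Mixed infections.** A reader might infer that mixed infections lose a pathogen in general. They do not: the definition is plural, so every mold in the last positive sample is kept. Nor can a later negative culture erase an isolate, because the rule looks for the last positive one.
- **A count of misclassified patients.** A reader might apply a guessed discordance rate to 24 patients and call the result misclassified. The documents give no rate, and some discordant patients would have the more credible isolate last.
- **The only evidence on rare molds.** A reader might infer this of the by-pathogen summaries. SAP 6.4.7 and 6.8.1 also list organisms by patient from the local and central laboratories. The listings do not correct the tables, however, and choosing organisms from them once outcomes are known in an open-label study is a choice better made in advance.
- **Appendices D and E grade diagnostic certainty, not causation.** This is true, and note 3 on blood cultures shows that body site alone does not settle the cause. It is still no argument for recency, which uses neither diagnostic weight nor adjudication.
- **DRC Charter not available.** The DRC may already record a causative organism. SAP 3.5 and 5.3.3 do not use it if so.

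**Conclusion.** The point holds within limits. The SAP states an explicit rule, and for patients whose pre-dose samples grow different molds that rule can replace a sterile-site isolate with a later airway one or drop a mold found only earlier. The consequence is confined to descriptive by-pathogen mortality and response and to the baseline pathogen table. No hypothesis test or decision depends on them, and the 91.1% power, overall mortality and overall global response are unaffected.

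The number of patients affected is unknown. The only general statement of size is the 1/k bound for one patient removed. The worked shifts of 13.3 points down (33.3% to 20.0%) or 6.7 points up (33.3% to 40.0%) rest on an assumed 6 rare-mold patients with 2 deaths. It is worth correcting because small rows are sensitive to one patient and the correction is cheap, not because the trial's main conclusion is at risk.

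**What to change.** Reword SAP 3.5 and 5.3.3 before the SAP is finalized. Define baseline pathogen(s) as all qualifying molds from any pre-dose culture of the qualifying episode, applied in this order:

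1. If a sterile-site culture meeting Appendix D is positive, use its mold or molds. Show discordant airway isolates in the listing only. An *Aspergillus* blood culture of the kind described in note 3 should not take priority.
2. Otherwise, use all molds from the qualifying airway or sinus cultures.
3. Put patients who still have more than one mold after steps 1 and 2 in a 'mixed' row.

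Where the DRC's adjudication already names a causative organism, use it to settle discordant cases. Applying the steps in sequence gives each patient with a qualifying culture one row: a tissue mold with a different later airway mold is classed by the tissue mold, not as mixed.

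No new samples are needed. Isolates already go to the central laboratory, and the DRC already adjudicates the diagnosis. The cost is SAP wording, slightly more derivation work and possibly one more small row in tables that are already thin. Patients with no positive culture at all are a separate matter, which this wording does not resolve.
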